6.3.4 Lumbar Puncture for Immune and Biomarker Analysis

Lumbar punctures (LP) will occur at Screening, Week 12, and Week 52. Lumbar punctures will be performed after a minimum of an 8 hour fast. The subject will be positioned seated or lying on their side on the examination table. Standard protocols will be used employing palpation to identify the L3-4, L4-5 or L5-S1 vertebral interspaces, sterile conditions, local lidocaine anesthesia, and use of standard of care spinal needles. Clinical judgement will be used to determine the optimal spinal needle type/size for each participant. Lumbar punctures will be performed by qualified, experienced practitioners. Approximately 25 mL of CSF at each visit will be collected. A small portion of this volume will be used for analysis of cell count with differential, total protein, and glucose. The remainder will be spun and cells isolated from supernatant. Supernatant will be frozen for later immunoassays. Cells will be frozen for later biochemical analyses. Subjects will also complete a brief REDCap survey after the LP in which they will answer questions about the tolerability of the procedure. After the LP is complete, subjects will be given time to eat breakfast or have a snack before continuing with the visit.

If a subject has difficult back anatomy or is particularly overweight, and the physician or nurse practitioner does not feel comfortable performing the LP because they are not able to locate the proper lumbar landmarks, the subject will be scheduled to undergo the LP under fluoroscopy at MGH Interventional Radiology. Fluoroscopy time will vary person to person. The average radiation dose is 0.18 millisieverts (mSv), or the equivalent of 21 days of natural background radiation, for each lumbar puncture done under fluoroscopy.

CSF samples will be de-identified, codified, and stored on-site at the MADRC/MIND biorepository at the [name] Lab. CSF samples will be stored for research until they are used, damaged, or otherwise unfit for analysis. Some biomarker analyses may be done at Harvard-affiliated core labs.

6.3.4.1 Sending CSF Samples to Research Collaborators Outside Mass General Brigham

CSF cell samples may be sent to Merck & Co. and Active Motif, Inc. for analyses. Samples will be de-identified with a study code and visit date.

6.3.5 Injection Site Monitoring

Prior to the first injection, both deltoids will be inspected to confirm there is no evidence of previous BCG vaccination and no obvious symptoms that would contraindicate vaccine injection. At the Week 4 visit, prior to the second injection, the vaccination site will be inspected for any signs of local infection. At Week 12, Week 26, and Week 52 and if indicated by subject-reported AEs, the site(s) of vaccination will be examined, and any visible reactivity will be recorded. In addition, photographs of the injection site may be taken using an MGB-approved and encrypted device. Photographs will be stored on the MGB Dropbox.

6.3.6 Magnetic Resonance Imaging (MRI)

Based on investigator discretion and cognitive ability, up to 12 participants over 60 years old may be invited to participate in an optional 3T structural and functional MRI at Week 1 and Week 52 to assess the effect of the study vaccine on regional brain volumes, cerebral perfusion, and structural and functional brain connectivity. Each scan will include high resolution T1-weighted multi-echo MPRAGE for volumetric analysis, task-free blood oxygen level dependent (BOLD) sequences to measure resting neural connectivity, diffusion tensor imaging (DTI) to quantify white matter structural connectivity, T2-weighted fluid attenuated inversion recovery (FLAIR) sequence to identify brain lesions, including cortical and periventricular lesions, and susceptibility-weighted imaging (SWI) to identify micro-hemorrhages and venous connectivity in lesions, and pseudo-continuous arterial spin labeling (pCASL) to quantify regional cerebral blood flow (a marker of resting cerebral perfusion).

6.4 Neurocognitive Assessments

6.4.1 Montreal Cognitive Assessment (MoCA)

The Montreal Cognitive Assessment (MoCA) is a commonly utilized questionnaire in clinical trials and research settings to measure levels of cognitive impairment.⁵⁰ The MoCA measures five areas of cognitive function: orientation, visuospatial, attention and calculation, recall, and language. The MoCA (version 8.1) will take approximately 15 minutes to complete. The MoCA will be administered at the Screening visit (version 8.1) to determine subject eligibility (MoCA ≥ 8) and repeated at Week 12 (version 8.2), Week 26 (version 8.3), and Week 52 (version 8.1).

6.4.2 Repeatable Battery for the Assessment of Neuropsychological Status Update (RBANS)

The RBANS⁵¹ is a commonly used 25-minute, standardized neurocognitive battery. The RBANS measures five neurocognitive domains, with twelve subtests measuring cognitive decline or improvement with immediate memory (List Learning and Story Memory), visuospatial/constructional (Figure Copy and Line Orientation), language (Picture naming and Semantic Fluency), attention (Digit Span and Coding), and delayed memory (List Recall, List Recognition, Story Memory, and Figure Recall). The RBANS has been shown to be effective at both detecting and characterizing forms of dementia. The Delayed Memory domain has been shown to be particularly sensitive to discriminating mild cognitive impairment (MCI) due to Alzheimer's disease from controls, and also is predictive of cerebral amyloid burden. The RBANS will be administered at Week 1 (form a), Week 12 (form b), Week 26 (form c), and Week 52 (form a).

6.4.3 Clinical Dementia Rating (CDR) Scale

The CDR is a 5-point scale used to characterize six domains of cognitive and functional performance applicable to Alzheimer disease and related dementias using a 30-minute semi-structured interview: Memory, Orientation, Judgment & Problem Solving, Community Affairs, Home & Hobbies, and Personal Care. The necessary information to make each rating is obtained through a semi-structured interview of the patient and an informant (study partner). The CDR table provides descriptive anchors that guide the clinician in making appropriate ratings based on interview data and clinical judgment. In addition to ratings for each domain, an overall CDR score may be calculated using an algorithm. This score is useful for characterizing and tracking a patient's level of impairment/dementia: 0 = Normal; 0.5 = Very Mild Dementia; 1 = Mild Dementia; 2 = Moderate Dementia; 3 = Severe Dementia. The CDR scores will be converted into a 'sum of boxes (CDR-SOB)' score, which is more sensitive in distinguishing between individuals with milder declines in functioning as it increases the range of possible scores⁵². The CDR will be administered at Screening to determine subject eligibility (CDR between 0.5-2 inclusive) and will be repeated at Week 52. The portion of the CDR completed with the study partner may be completed over the phone at Week 52.

6.4.4 DCT Clock

DCT clock, a digitized version of the standard pen and paper neuropsychological clock drawing test, is a non-invasive, computer-based cognitive assay. The DCT clock application is preloaded onto the iPad. The test involves participants drawing two clock faces on an iPad, with a digital pen that precisely tracks and records drawing behavior. The positional data generated during this assessment is then analyzed by DCT's proprietary algorithms that evaluate hundreds of features captured in the pen stroke information. By comparing test results to normative data, the system then determines whether the test was within normal limits and provides a detailed breakdown of performance on the various cognitive tasks evaluated during the test.

6.5 Neuropsychiatric Assessments

6.5.1 Neuropsychiatric Inventory Questionnaire (NPI-Q)

The NPI-Q⁵³ will rate symptoms in 12 sub-domains of behavioral functioning including: hallucinations, delusions, agitation, dysphoria, anxiety, euphoria, apathy, disinhibition, irritability, aberrant motor activity, eating abnormalities, and night-time behavioral alternations. The NPI-Q is administered to an informant (study partner) and will be done at Week 1, Week 12, Week 26, and Week 52. The NPIQ may be completed over the phone at Week 12, 26, and 52.

6.5.2 Functional Activities Questionnaire (FAQ)

The FAQ^{12,54} is a brief rating scale used to determine a subjects' level of functional independence when performing a range of instrumental activities of daily living (IADLs), with repeat assessments useful for monitoring performance in these areas over time. The FAQ total score (ranging from 0-30) reflects the sum of ordinal ratings (0 = fully independent, 1 = has difficulty but does by self, 2 = requires assistance, and 3 = dependent) across ten items assessing a variety of functional activities (i.e., preparing a balanced meal, financial management skills, and shopping), with higher scores indicating increasing levels of dependence. For activities not normally undertaken by a person, a score of 1 is assigned if the subject would be unable to complete the task if required, or a score of 0 is assigned if the subject believes they could successfully carry out the task if needed. Overall, the FAQ is a sensitive marker of functional impairment among individuals with varying dementia severity and has been shown to differentiate mild cognitive impairment from early dementia due to Alzheimer's Disease with 80% sensitivity and 87% specificity. The FAQ demonstrates high reliability (exceeding 0.90), takes about 5 minutes to complete, and requires limited rater training to administer. The FAQ is administered to an informant (study partner) and will be done at Screening, Week 12, Week 26, and Week 52.

6.5.3 Hospital Anxiety and Depression Scale (HADS)

The HADS (Hospital Anxiety and Depression Scale) aims to measure symptoms of anxiety and depression. HADS is a 14-item scale with seven items each for anxiety and depression subscales. Scoring for each item ranges from zero to three. A subscale score >8 denotes anxiety or depression. HADS will be administered at Week 1, Week 12, Week 26, and Week 52.

7 STUDY INTERVENTION ADMINISTERED

Table 3. Summary of Investigational Products

	Investigational Products	
Product Name:	Bacillus Calmette-Guérin (BCG) vaccine [Tokyo BCG (JBL, Tokyo, Japan)]	Diluent (0.9% sodium chloride for injection)
Dosage Form:	For intradermal injection	For intradermal injection
Unit Dose	$0.36-3.9 \times 10^6$ colony forming units(CFU)/injection of 0.1ml	0.1 mL
Route of Administration	Intradermal injection	Intradermal injection
Physical Description	sterile, freeze-dried	BCG diluent
Manufacturer	Japan BCG Laboratory (JBL)	Supplied by MGH clinical trials pharmacy (manufacturer varies)

7.1 Study Drug

Japan BCG is an approved drug in Japan and has been sanctioned by UNICEF and WHO as a standard vaccine for the prevention of tuberculosis. BCG has been administered for this purpose for over 100 years on a global basis, with typical distributions of over 50,000,000 doses to newborns per year. The vaccine has also been approved and utilized for treatment of bladder cancer for the past 30 years.

JBL is the manufacturer of BCG products produced from the BCG strain of Tokyo 172-1 and [name] and MGH oversee and regulate this manufacturing. This protocol will be reviewed by the Japan BCG Laboratory ethics committee prior to commencement of study activities. Drug-related contracting will occur through [name] who maintains the Master Drug File, coordinates various IND filing around this vaccine and will interface with regulatory affairs management.

The study drugs (BCG vaccine and diluent) are manufactured by Japan BCG Laboratory and supplied by the MGH Clinical Trials Pharmacy (manufacturers vary), respectively, and will be managed and stored by the study pharmacist in the [name] lab according to the directions provided by the manufacturer in the approved product labeling. The same study pharmacist and study drug have been used for the past 6 years in [name] protocol #2013P002633 in addition to the pilot protocol #2020P002042.

Japan BCG is a freeze-dried preparation made from the Tokyo 172 strain of *Mycobacterium bovis* Bacillus Calmette and Guérin (BCG). Japan BCG is an attenuated BCG product derived from the original attenuated BCG generated by Albert Calmette and Camille Guerin at the Pasteur Institute.

7.2 Study Drug Packaging and Labeling

The Japan BCG drug product is a sterile, freeze-dried preparation of BCG.

This drug is stored at 2-8°C.

7.3 Study Drug Preparation

The BCG vaccine is supplied as a 10-dose ampoule. For reconstitution, 1.0 ml of sterile saline is added to the 10-dose ampoule. Each 0.1ml dose is drawn by syringe from the ampoule following reconstitution and administered intradermally. Once reconstituted, the pharmacy provides the study clinic with the pre-filled syringe in a covered surgical tray to prevent light exposure. If the prepared syringe cannot be immediately administered, it will be temporarily stored at 4°C until administration (< 1 hour from reconstitution). The BCG vaccine will be prepared by the study pharmacist at MGH.

Each ampoule may be used for a maximum of two study participants in this study. The ampoule will be reconstituted, and two syringes may be drawn at the same time. As above, the prepared syringes will be covered and stored at 4°C until administration within 1 hour of reconstitution. The remaining unused volume in the ampoule will not be used for additional patients in this trial.

7.4 Dosage and Administration

All subjects will be consented by a study clinician before any of the following procedures are done. The skin site (deltoid region, alternating between first and second dose) is first cleansed with an alcohol or acetone sponge and allowed to dry thoroughly. Next, $0.36-3.9 \times 10^6$ colony forming units (CFU), reconstituted by the study pharmacist in 0.9% saline diluent within 1 hour, will be administered intradermally via a 15mm, 26-gauge needle.

Dose selection is based on published data illustrating that two doses of BCG in autoimmune type 1 diabetes confer the immune regulatory/inflammation modulation properties that are of interest in the present study. Specifically, administration of two doses in type 1 diabetes is associated with short term changes in biomarkers with 22 weeks of observations.³⁶ Moreover, two doses of BCG resulted in a clinical correction of HbA1c in type 1 diabetes with stable correction of disease process for 8 years.³⁷

7.5 Study Drug Accountability

Vaccine accountability will be maintained by the study pharmacist.

7.6 Study Drug Handling and Disposal

Vaccine handling and disposal will be managed by the study pharmacist.

7.7 Contraindications and Warnings

7.7.1 Prohibited Medications

An Open Label Trial to Evaluate the Effects of BCG Immunization on Biomarkers of Inflammation/Immune Response and Alzheimer's Disease in Adults with Mild Cognitive Impairment and Mild-to-Moderate Dementia due to Alzheimer's Disease
Version Date#: October 13, 2022/Version 3.3

Treatment with the following medications during the study is prohibited:

- Metformin
- Aspirin > 160 mg/day
- Chronic daily NSAIDS
- Immunosuppressants including calcineurin inhibitors, corticosteroids, or biological or cytotoxic immunosuppressants (e.g. imuran, methotrexate, cyclosporine, etanercept, infliximab)
- Antibiotics within 14 days of immunizations
- Administration of live vaccine within 30 days of screening visit or BCG immunizations
- Administration of non-live vaccine within 14 days of screening visit or BCG immunizations

7.7.2 Warnings

BCG contains live, attenuated mycobacteria, and carries risk for adverse consequences particularly in immunocompromised individuals for whom the attenuated strain could become pathogenic as described below (section 9.1, BCG vaccine risks).

8 BIOSTATISTICAL ANALYSIS

8.1 Sample Size

A sample size of approximately 15 subjects was chosen based on feasibility and is not based on statistical considerations. The primary objective of this early-phase trial is to measure safety and target engagement. While there is no ‘best practice’ method of determining target engagement of the BCG vaccine, the method that best takes advantage of the collected biomaterials is the *in-vitro* IFN-gamma release assay. PBMCs are stimulated and after several days the culture media is tested for presence of the IFN-gamma cytokine. In a previously published study, it was demonstrated a significant IFN-gamma release difference associated with BCG treatment in n = 14 subjects⁵⁵.

8.2 Safety Endpoints

The primary safety endpoint will be the incidence of treatment emergent Grade II-IV adverse events.

Other safety endpoints are:

- Incidence and severity of treatment emergent adverse events (AEs)
- Clinical laboratory tests
- Vital signs
- Physical examinations
- Use of concomitant medications for treatment of AEs

All concomitant medications will be tabulated according to drug class and preferred term using the WHO dictionary. The safety data will be summarized by treatment group. Treatment AEs will be coded and graded using MedDRA grading criteria. The treatment groups will be compared with respect to occurrence of each adverse event and incidence of Grade II/IV adverse events. Withdrawal, abnormal laboratory tests, vital signs and use of concomitant medications used for treatment of AEs will be assessed to characterize the safety profile of BCG. Descriptive statistics denoting the changes from baseline to the final assessment visit with respect to key laboratory parameters and vital signs will also be provided.

Adverse events (AE) occurring after the start of study drug dosing at Baseline will be summarized descriptively. All AEs will be coded according to system organ class (SOC) and preferred term (PT) using a Medical Dictionary for Regulatory Activities (MedDRA) dictionary. Summary tables showing the number of subjects and percent within each category will be generated for each of the following types of adverse events and its relationship to study treatment (related to study treatment):

- All events
- Serious events
- Deaths
- Events leading to withdrawal
- Severe events

Treatment AEs will be coded and graded using MedDRA grading criteria. and compared with respect to occurrence of each adverse event and incidence of Grade II/IV adverse events. Total number of adverse events will be compared between groups using Fisher's exact test. Any treatment AE still present upon completion of treatment (including early discontinuation) should be monitored until resolution or until the AE is declared a chronic condition. AEs will be monitored until they become chronic or have completely resolved.

Laboratory parameters will be summarized by visit; descriptive statistics denoting the changes from baseline to the final assessment visit with respect to key laboratory parameters and vital signs will also be provided. Frequencies of high and low values with respect to the normal range will be displayed, as will shift tables comparing each treatment visit and Baseline visit by time point.

Vital signs will be summarized across groups by visit using descriptive statistics, and at each outcome visit and at end of study. Physical examination findings and number of subjects will be summarized as the count and percentage of subjects by eCRF pre-defined categories at last visit. Change from baseline at last visit will be summarized in a shift table comparing baseline and last visit results. Concomitant medications will be summarized, drug class and preferred term.

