3 STUDY DESIGN

3.1 Overall Study Design and Plan

This single-site, open-label trial will investigate the effects of BCG vaccination on IIR and AD biofluid biomarkers, magnetic resonance imaging (MRI) biomarkers, and neurocognitive/behavioral functioning over a one-year period in older adults with mild cognitive impairment (MCI) to mild-to-moderate dementia due to AD. This study will also gather data on tolerability and safety. Safety will continue to be followed in the second year by phone.

Up to twenty five participants meeting eligibility criteria will be enrolled. Each participant will receive two intradermal BCG vaccinations spaced 4-6 weeks apart and will be evaluated 12, 26, and 52 weeks after the initial immunization. Cerebrospinal fluid (CSF), blood, MRI (in a subset of patients), and neurocognitive/behavioral assessments will be collected at Screening (CSF, blood, and cognitive/behavioral), Week 1 (MRI and cognitive/behavioral), Week 4 (blood), Week 12 (CSF, blood, and cognitive/behavioral), Week 26 (Blood and cognitive/behavioral) and Week 52 (all) to assess biomarkers and safety. Safety measures, including updated medical history and adverse events, will be collected at Week 78 and Week 104.

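### Section 8.2 plans between-group safety comparisons and a Fisher test in a trial where everyone receives BCG, and the primary Grade II-IV endpoint is missing from the listed tables

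*Combined protocol and SAP*

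**What the plan says.** Section 3.1 describes a single-site, open-label trial: "Each participant will receive two intradermal BCG vaccinations spaced 4-6 weeks apart". Section 6.1.1 lets participants of an earlier randomised trial roll over. They are unblinded, and those first given placebo restart at a new Day 1 and then receive BCG. No comparison is attached to that arrangement.

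Section 8.2 sets the endpoint: "The primary safety endpoint will be the incidence of treatment emergent Grade II-IV adverse events". It then gives instructions that presuppose more than one arm:

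- "The safety data will be summarized by treatment group".
- "The treatment groups will be compared with respect to occurrence of each adverse event and incidence of Grade II/IV adverse events". Similar wording recurs later in the section.
- "Total number of adverse events will be compared between groups using" Fisher's exact test.
- "Vital signs will be summarized across groups by visit using descriptive statistics".

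The same section also contains text that works for one arm: "Adverse events (AE) occurring after the start of study drug dosing at Baseline will be summarized descriptively". It promises tables of number and percent of subjects for five categories: all events, serious events, deaths, events leading to withdrawal, and severe events.

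On grading, Section 8.2 says "Treatment AEs will be coded and graded using MedDRA grading criteria". Section 3.3.1 uses the FDA toxicity scale for changes from baseline, and Section 11.3.3 records severity in three levels (mild, moderate, severe).

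**The concern.** A between-group analysis needs a second group. The plan has none, and it does not say that roll-over status or earlier allocation should serve as one. Whoever runs the analysis must either drop these instructions or choose groups after the data are in hand, which would make the comparison post hoc.

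This matters most for the primary safety endpoint. Safety is the first primary objective in Section 3.2, yet the one planned analysis that mentions Grade II-IV incidence is the comparison that cannot be done. The denominator and any measure of precision are left open. So is the start of counting for people who first received placebo.

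**Working it through.** The plan states no power, error rate or expected event rate for safety. Section 8.1 sets about 15 participants on feasibility grounds, so there is no figure of the plan's own to reproduce. The check compares the sections and then shows what a one-arm summary would deliver.

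**1. Is there a comparator?** Section 3.1: everyone receives BCG. Section 6.1.1: former placebo recipients move to BCG, with no comparison, time window or numbers given. Section 3.3.2 mentions comparing biomarkers between groups but defines none, and it does not concern safety. The answer is no.

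**2. Can Fisher's test be applied?** With x of n affected in one arm and an empty second row, the table is [[x, n−x], [0, 0]]. Once the margins are fixed, only this table is possible, so its probability is C(n,x)·C(0,0)/C(n,x) = 1 and p = 1. The odds ratio is (x·0)/((n−x)·0) = 0/0, which is undefined. Running it for 0, 3 and 7 affected at n = 12, 15 and 25 gave p = 1.0 and an undefined odds ratio each time. This shows only that the test does not apply.

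**3. Do the remaining tables give the primary endpoint?**

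| Listed category | Gives the Grade II-IV proportion? |
|---|---|
| All events | No: also includes Grade I |
| Serious events, deaths, events leading to withdrawal | No: defined by other criteria |
| Severe events | No: omits Grade II |

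A Grade II event that is not serious and does not lead to withdrawal is counted only under all events.

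**4. When does counting start?** Section 8.2 counts from dosing at Baseline. Section 6.2.2 sets Day 1 at the first BCG injection. Section 6.1.1 uses Baseline for the earlier trial's visit, at which some people received placebo, and makes their Day 28 visit the new Day 1. For those people the two readings differ by about 28 days.

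**5. Do the grading descriptions agree?** Three are in use (Sections 3.3.1, 8.2 and 11.3.3). Section 5.5 links grade 3 with severe. If moderate means Grade II and severe means Grade III or above, then moderate plus severe gives the pooled Grade II-IV numerator. The plan does not state that mapping.

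**6. What would a one-arm summary show?** Exact (Clopper-Pearson) two-sided 95% limits, with n = 15 from Section 8.1:

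- 0 affected (illustrative): upper limit = 1 − 0.025^(1/n) = 1 − 0.025^(1/15) = 21.8%.
- 5 affected (assumed; the plan gives no expected rate): the lower limit is the 2.5% quantile of Beta(5, 11) = 11.8%, and the upper limit is the 97.5% quantile of Beta(6, 10) = 61.6%.
- 0 affected at the enrolment ceiling of 25: 1 − 0.025^(1/25) = 13.7%. This is a best case, because Section 6.2.1.3 counts everyone who signs consent as enrolled, including screen failures.

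**The case against.** The strongest reply is that little is lost. An incidence is already a one-arm quantity, AEs are to be summarised descriptively, and participant-level tables are planned. An analyst would see that the group sentences cannot be run and leave them out. This stands in large part. A reader might infer that the plan has no usable one-arm safety analysis, and Section 8.2 does not support that. What is missing is a Grade II-IV row, its denominator and an interval.

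A reader might also take Fisher's test to be the planned test of the primary endpoint. The text applies it to the total number of AEs. Grade II/IV incidence is to be compared between groups, with no test named. If the total means events and not people, Fisher's test would also treat repeated events in one person as independent, but the wording does not settle which is meant.

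Roll-over participants might be offered as the missing groups. A comparison by earlier allocation over Days 1 to 28 would indeed be BCG against placebo, but Section 6.1.1 does not set one up.

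It is tempting to say that a three-level severity record, with no Grade IV, makes the endpoint impossible to derive. The endpoint pools Grades II to IV, so under the mapping in step 5 the numerator is unaffected. The gap is the unstated mapping.

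On AE start, Sections 6.2.2 and 6.1.1 read together point to the first BCG dose, and AEs are collected from consent (Section 11.3.1), so no data are lost. The ambiguity is real but narrow. It comes from the use of Baseline for the placebo visit and affects only former placebo recipients, whose number is not given.

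**Conclusion.** The point holds and should be fixed before analysis. The treatment-group summaries, between-group comparisons and Fisher test in Section 8.2 cannot be carried out in the trial that Section 3.1 describes. The only analysis naming the primary safety endpoint is among them, and Grade II-IV is absent from the listed tables. Descriptive AE reporting survives, which limits the damage.

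The p-value of 1 should not be read as a measure of harm. Likewise, the intervals show the imprecision of a sample this small and not a cost of the wording: the upper limit is 21.8% with 0 of 15 affected, and the range is 11.8% to 61.6% with an assumed 5 of 15. They rest on 15 people being dosed and on illustrative counts. The 12 expected completers in Section 4.2 are not the right denominator for an analysis of everyone dosed.

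**What to change.** In Section 8.2, delete the by-treatment-group summary, the between-group comparison in both places, and the Fisher test. Replace them with text along these lines:

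*Among all participants who receive at least one BCG dose, the number and proportion with one or more treatment-emergent Grade II-IV AEs will be reported with an exact (Clopper-Pearson) 95% confidence interval. Treatment-emergent AEs are counted from the first BCG dose, which is the new Day 1 for former placebo recipients. AEs between a placebo dose and the new Day 1 are listed separately. Any display by roll-over status is descriptive, with no test.*

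Add Grade II-IV as a row in the AE tables. Reconcile the grading descriptions in Sections 3.3.1, 8.2 and 11.3.3 by stating how each maps to Grades II-IV. Writing Grade II-IV consistently, and removing the reference to groups from the vital-signs sentence (which could simply mean pooled), is tidying only.

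The cost is a wording change in Section 8.2 and one statement on grading, with no extra data for the pooled endpoint. Reporting Grade IV separately would go further: if severity is recorded only in three levels, it would need a change to the AE form or regrading.
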